APPENDIX 2. SCHEDULE OF ASSESSMENTS - AML SUBJECTS ONLY - MONOTHERAPY

	Screening ^b	Cycle 1				Cycle 2		Cycle 3 and Subsequent Cycles ^c	End of Study ^d
Day(s) ^a	-28 to -1	1 ^a	2	8	15	1	15	1	30 days (± 3 days) post last dose
Informed consent	X								
Medical history	X								
Physical examination	X	X							X
Symptom-directed exam ^e				X	X	X		X	
Vital signs ^f	X	X		X	X	X		X	X
Height	X								
Weight	X					X		X	X
ECOG performance status	X	X				X		X	X
Pregnancy test ^g	X	X				X		X	X
HIV testing ^h	X								
Hepatitis B and C testing ⁱ	X								
Adverse events ^j		X	X	X	X	X	X	X	X
Concomitant medication ^k	X	X	X	X	X	X	X	X	X
ECG ^l	X	X		X	X	X			X
CBC with differential ^m	X	X		X	X	X	X	X	X
Serum chemistry ⁿ	X	X	X	X	X	X	X	X	X
TLS risk assessment and monitoring ⁿ	X	X	X						
Coagulation ^o	X		X		X	X		X	X
Urinalysis (dipstick) ^p	X					X			X
Issue and assess compliance diary ^q		X				X		X	
Dispense study drug ^r		X				X		X	
PK Sampling (all subjects) ^s		X	X	X	X	X			
Disease assessment / Bone marrow ^t	X					X		X	X
Cytogenetics ^u	X								
Molecular mutations ^v	optional								
Blood for PD/biomarker assays ^w		X	X	X	X				X

APPENDIX 2. SCHEDULE OF ASSESSMENTS - AML SUBJECTS ONLY - MONOTHERAPY (CONTINUED)

Abbreviations: AML = acute myeloid leukemia; ALP = alkaline phosphatase; ALT = alanine aminotransferase; ANC = absolute neutrophil count; aPTT = activated partial thromboplastin time; AST = aspartate aminotransferase; BP = blood pressure; BUN = blood urea nitrogen; CBC = complete blood count; CR = complete response; CT = computed tomography; ECG = electrocardiogram; ECOG = Eastern Cooperative Oncology Group; EOS = End of Study; Hct = hematocrit; HCV Ab = hepatitis C virus antibody; Hgb = hemoglobin; HIV = human immunodeficiency virus; HR = heart rate; ICF = informed consent form; INR = international normalized ratio; LDH = lactate dehydrogenase; MCH = mean corpuscular hemoglobin; PCR = polymerase chain reaction; PD = pharmacodynamic; PK = pharmacokinetic; PT = prothrombin time; RBC = red blood cell; TLS = tumor lysis syndrome; WBC = white blood cell.

- a. Study Assessment Day(s)** – C1D1 and visits when blood for pharmacodynamic/biomarker studies are collected should be conducted Monday through Wednesday if possible so that specimens can be shipped for receipt no later than a Friday. There is ± 3 -day window allowable for each clinic visit during Cycle 1. Following Cycle 1, the allowable window is up to 7 days prior and 2 days after the scheduled clinic visit and its associated assessments.
- b. Screening** – Screening assessments are to be performed within 28 days of first dose of voruciclib. Laboratory assessments need not be repeated on Day 1 if performed within the prior 72 hours. Physical examination need not be repeated on Day 1 if performed within the prior 7 days. Some tests performed prior to obtaining ICF (e.g., CT scan, bone marrow biopsy) may not need to be repeated for the study as long as they were performed within the allowed screening window.
- c. Cycle 3 and subsequent cycles, and EOS** – All cycles after Cycle 3 should follow the same schedule of activities as Cycle 3.
- d. EOS** - The End of Study (EOS) visit will occur 30 days (± 3 days) from the last day of voruciclib administration (or prior to starting a new treatment if urgent treatment is required).
- e. Symptom-directed exam** – performed only as needed/indicated, based on interim history
- f. Vital signs, Height and Weight** – includes systolic and diastolic blood pressure (BP), heart rate (HR), and body temperature. Height collected at Screening visit only.
- g. Pregnancy test** – Serum pregnancy test in females of childbearing potential at screening, urine pregnancy test Day 1 of each cycle and at EOS.
- h. HIV testing** – HIV antibody testing is required.
- i. Hepatitis B and Hepatitis C testing** – Hepatitis B core antibody, surface antibody and surface antigen, and hepatitis C virus antibody (HCV Ab) tests are required. Hepatitis B polymerase chain reaction (PCR) is required if hepatitis B core antibody and/or surface antigen is positive. Hepatitis C PCR is required if HCV Ab test is positive.
- j. Adverse events** – Recorded from the first dose of voruciclib and continue until 30 days after the last dose, or until a subsequent anti-cancer therapy is initiated.
- k. Concomitant medications** – Recorded from 28 days prior to Cycle 1 Day 1 through 30 days after the last dose of voruciclib, or until a subsequent anti-cancer therapy is initiated.
- l. ECG** – 12 lead ECGs performed in triplicate (approximately 2–5 minutes apart while the subject is resting) at screening, Cycle 1 Day 1, Day 8 (24 ± 3 hours after the preceding last dose in Cohorts 9-11), and Cycle 1 Day 15 (pre-dose and 4 hours post-dose voruciclib in Cohorts 1-5, and 24 ± 3 hours after the preceding last dose in Cohorts 6-8), and at Cycle 2 Day 1 (pre-dose voruciclib) and EOS (single triplicate post-dose).
- m. CBC with differential** – WBC, ANC, RBC, Hgb, Hct, platelets, MCH, and differential.
- n. TLS monitoring/ Serum chemistry** – Chemistry for monitoring of TLS risk (including potassium, uric acid, phosphorus, calcium and creatinine) will be performed as indicated in the TLS management plan (see [Appendix 9](#)) and as clinically indicated. Subjects must be assessed for TLS risk during screening and before first dose of voruciclib (monotherapy) on Cycle 1 Day 1. Standard chemistry panel to include glucose, BUN, creatinine, sodium, potassium, chloride, calcium, phosphate, uric acid, CO₂, ALP, AST, ALT, total bilirubin, total protein, albumin, LDH.
- o. Coagulation** – aPTT, PT, and INR.

APPENDIX 2. SCHEDULE OF ASSESSMENTS - AML SUBJECTS ONLY - MONOTHERAPY (CONTINUED)

p. Urinalysis – Dipstick.

q. Issue and Assess Compliance Diary – Compliance diary to record voruciclib administration. Returned diaries are to be assessed for study drug compliance. New compliance diary to be dispensed with each dispensing of voruciclib.

r. Dispense study drug – Voruciclib is administered orally once a day on dosing days, on an empty stomach at least 1 hour prior to food or 2 hours after food at approximately the same time each day. On days of PK sampling, subjects should be instructed to not take voruciclib until after the pre-dose PK sample is collected.

As of Amendment 7, voruciclib will be administered on an intermittent dosing schedule of 2 week on/2 week off (IS2w,2w) or 1 week on/3 weeks off (IS1w,3w), in the 28-day cycle. Note that voruciclib is taken daily on dosing days only, i.e., days 1 through 14 on IS2w,2w, and on days 1 through 7 only on the IS1w,3w regimen. Therefore, there is no dosing on Day 8 on IS1w,3w and on Day 15 of the IS2w,2w cycle.

s. PK sampling – Unless stated otherwise, pre-dose specimens should be within 2 hours prior to dosing, post-dose samples within ± 30 minutes of the sampling time. For monotherapy for Cohorts 1-5:

- Cycle 1 Day 1: pre-dose (before voruciclib dose is taken); and at 4- and at 6- hours post-dose
- Cycle 1 Day 2: pre-dose (i.e., 24 hours after the Cycle 1 Day 1 voruciclib dose)
- Cycle 1 Day 8: pre-dose (24 hours after the preceding last dose, before voruciclib is taken)
- Cycle 1 Day 15: pre-dose (before voruciclib dose is taken); at 4- and at 6- hours post dose

For monotherapy Cohorts 6a-11a (IS dosing):

- Cycle 1 Day 1: pre-dose and at 4- and at 6- hours post-dose
- Cycle 1 Day 2: pre-dose (24 hours after the preceding last dose)
- Cycle 1 Day 8: pre-dose (24 hours after the preceding last dose)
- Cycle 1 Day 15: 24 hours after the preceding last dose), if applicable [Day 15 samples only collected for the IS_{2w,2w} schedule]
- Cycle 2 Day 1: pre-dose

t. Disease assessment / Bone marrow – Bone marrow aspirate/biopsy and laboratory evaluation at screening, Cycle 2 Day 1, Cycle 3 Day 1, and Day 1 of every subsequent cycle until a CR or CRi is achieved after which bone marrow examinations are obtained if clinically indicated, and at EOS. Both biopsy and aspirate are recommended for disease assessment, but biopsy may be omitted if aspirate is considered to be sufficient. A fresh specimen of aspirate is to be obtained at each timepoint as described in the Study Manual and submitted to the central laboratory for pharmacodynamic/correlative study. The first blood specimen for pharmacodynamic/correlative studies must be taken prior to first dose on Cycle 1 Day 1 and a second specimen approximately 6 hours after the first dose on Day 1. Specimen may be taken up to 7 days prior to C1D1.

u. Cytogenetics – If abnormal cytogenetics at screening, repeat cytogenetics in a subject with CR/CRi to confirm a cytogenetic remission.

v. Molecular mutations/rearrangements analysis – Not required for the study. Collect if obtained as standard of care for a subject. If abnormalities identified at screening, repeat the test for the genetic marker by RT-qPCR or flowcytometry in a subject with CR/CRi to confirm CR with minimal residual disease.

w. Pharmacodynamic biomarker – The first blood specimen for Pharmacodynamic/biomarker assay must be taken prior to first dose on Cycle 1 Day 1, a second specimen approximately 6 hours post-dose on Day 1, and a third specimen pre dose on Day 2. The specimen obtained prior to starting study drug may be taken up to 7 days prior to C1D1. On Days 8 and 15 specimen will be taken prior to administration of study drug (Cohorts 1-5).

APPENDIX 3. SCHEDULE OF ASSESSMENTS - AML SUBJECTS ONLY – COMBINATION THERAPY

	Screening ^b	Cycle 1- Inclusive of Venetoclax Ramp-up ^c					Cycle 2		Cycle 3 and Subsequent Cycles ^d	End of Study ^e
	-28 to -1	1 ^a	2	3	8	14	1	14	1	30 days (± 3 days) Post Last Dose Study Drug
Informed consent	X									
Medical history/Prior Treatment/Demographics	X									
Physical examination	X	X								X
Symptom-directed exam ^f				X	X	X	X		X	
Vital signs ^g	X	X		X	X	X	X		X	X
Height	X									
Weight	X						X		X	X
ECOG performance status	X	X					X		X	X
Pregnancy test ^h	X	X					X		X	X
HIV testing ⁱ	X									
Hepatitis B and C testing ^j	X									
Adverse events ^k		X	X	X	X	X	X	X	X	X
Concomitant medication ^l	X	X	X	X	X	X	X	X	X	X
ECG ^m	X	X		X	X	X	X			X
CBC with differential ⁿ	X	X		X	X	X	X	X	X	X
Serum chemistry ^o	X	X	X	X	X	X	X	X	X	X
TLS risk assessment and monitoring ^o	X	X	X	X						
Coagulation ^p	X		X			X	X		X	X
Urinalysis (dipstick) ^q	X						X			X
Baseline chest x-ray ^r	X									
Issue and assess compliance diary ^s		X					X		X	
Dispense study drug(s) ^t		X					X		X	
Disease assessment, bone marrow aspirate ^u	X						X		X	X
Cytogenetics ^v	X									
Molecular mutations ^w	optional									
Blood for PD/biomarker assays ^x		X		X		X				
Blood for PK analysis	See specific PK collection timepoints in table below									

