4.3.2.1. Administration Schedules and Doses of Voruciclib + Venetoclax

Amendment 11 – IS_{2w,2w} Dosing Schedule

For Cycle 1 in combination cohorts 12–19, the dosing will be as follows ([Table 5](#)):

- Venetoclax will be ramped up starting with 100 mg on Day 1, 200 mg on Days 2–21, then 400 mg administered as a single agent on Days 22–28.
- Voruciclib dosing will be administered on Days 3–14 at the appropriate Cohort Dose ([Table 3](#)).

For Cycle 2 and beyond, the dosing will be as follows:

- Venetoclax 200 mg will be administered on Days 1–21, and 400 mg administered as a single agent on Days 22–28.
- Voruciclib at the cohort dose ([Table 3](#)) on Days 1–14.

Venetoclax should be taken with a meal and water. When both venetoclax and voruciclib are to be taken, venetoclax should be taken first with a meal followed by voruciclib at least 2 hours later (e.g., meal completed at 8 a.m. with venetoclax, dose of voruciclib taken after 10:00 a.m.). Voruciclib tablets must not be chewed, crushed, or broken.

Table 5: Administration Schedules of Voruciclib given in Combination with Venetoclax (IS_{2w,2w})

Administration Schedule of Voruciclib IS _{2w,2w} and Venetoclax per 28-day Cycle					
Cycle 1	Day 1	Day 2	Days 3 to 14	Days 15 to 21	Days 22 to 28
Venetoclax	100 mg	200 mg	200 mg	200 mg	400 mg
Voruciclib QD	-	-	Cohort dose	None	None
Voruciclib QOD ^a	-	-	50 mg ^a	None	None
Cycle 2 and beyond	Days 1 to 14		Days 15 to 21		Days 22 to 28
Venetoclax	200 mg		200 mg		400 mg
Voruciclib QD	Cohort dose		None		None
Voruciclib QOD ^a	50 mg ^a		None		None

Abbreviation: QOD = once every other day

^a For cohort 12, the dose of voruciclib will be 50 mg once every other day (QOD) on Days 3, 5, 7, 9, 11, and 13 of Cycle 1, and on Days 1, 3, 5, 7, 9, 11, and 13 of Cycle 2 and beyond.

Amendment 12 – IS_{3w,1w} Dosing Schedule

For Cycle 1 in combination cohorts 21–25, the dosing will be as follows (Table 6):

- Venetoclax dose will be ramped up starting with 100 mg on Day 1, 200 mg on Days 2–21, then 400 mg administered as a single agent on Days 22–28.
- Voruciclib dosing will be administered on Days 3–21 at the appropriate Cohort Dose (Table 4).

For Cycle 2 and beyond, the dosing will be as follows:

- Venetoclax 200 mg will be administered on Days 1–21, and 400 mg administered as a single agent on Days 22–28.
- Voruciclib at the cohort dose (Table 4) will be administered on Days 1–21.

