4.14. Prohibited Treatments and Concomitant Medications – Cautions and Prohibitions

4.14.1. Concomitant Medications with Voruciclib – Cautions and Prohibitions

In vitro studies have shown that voruciclib has the potential to inhibit cytochrome (CYP) CYP2C9, CYP2C19, CYP2D6, and CYP3A4, therefore, drugs with a narrow therapeutic

window that are metabolized by these enzymes should be avoided or used with caution (see [Appendix 7](#)).

Subjects receiving warfarin treatment are excluded, since voruciclib is highly protein bound and is a competitive inhibitor of CYP2C9 at higher concentrations and increased INR was a DLT in the previous Phase 1 studies. Subjects on study who initiate warfarin therapy must discontinue voruciclib.

Consistent with subject safety and comfort, administration of any prescription or over-the-counter (OTC) drug products other than study medication will be minimized during the study period. Subjects should be discouraged from use of herbal remedies, self-prescribed drugs, tobacco products, or street drugs during their participation in the clinical study and should be counseled to minimize use of alcohol or nonmedical marijuana.

If considered necessary for the subject's well-being, drugs for concomitant medical conditions or for symptom management may be given at the discretion of the Investigator. The Investigator's decision to authorize the use of any drug other than study drug will take into account subject safety, the medical need, the potential for drug interactions, the possibility for masking symptoms of a more significant underlying event, and whether use of the drug will compromise the outcome or integrity of the study.

Subjects will be instructed about the importance of the need to inform the clinic staff of the use of any drugs or remedies (whether prescribed, OTC, or illicit) before and during the course of the study.

No other anti-cancer therapeutics or investigational agents are permitted during the study treatment period, except for hydroxyurea or anthracycline for the treatment of DS and to manage rapidly rising white blood cell counts in Cycles 1 and 2 only in patients with AML. Palliative radiotherapy is permitted after Cycle 1 but should be minimized and used for control of local tumor-related symptoms only.

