APPENDIX 3. SCHEDULE OF ASSESSMENTS - AML SUBJECTS ONLY – COMBINATION THERAPY (CONTINUED)

- p. Coagulation** – aPTT, PT, and INR.
- q. Urinalysis** – Dipstick.
- r. Baseline chest x-ray** – recommended if the subject has not had recent chest imaging.
- s. Issue and Assess Compliance Diary** – Assess returned diaries for study drug dosing compliance. New compliance diary to be dispensed with each dispensing of study drug.
- t. Dispense study drug** – Venetoclax is administered orally once daily to be taken with food and water. Voruciclib is administered orally once a day on dosing days, at least 2 hours after venetoclax. On days of PK sampling (for PK sampling schedules refer to [Section 9.14.2](#)), subjects should be instructed to not take venetoclax or voruciclib until after the pre-dose PK sample is collected.
- As of Amendment 11, voruciclib will be administered on an intermittent dosing schedule of 2 week on/2 week off (IS_{2w,2w}) in the 28-day cycle. Note that voruciclib is taken once daily on dosing days only (i.e., Days 1 through 14 on IS_{2w,2w}), with the exception of Cohort 12 which is taken every other day (i.e., Days 3, 5, 7, 9, 11, and 13 of Cycle 1 and Days 1, 3, 5, 7, 9, 11, and 13 of Cycle 2 and beyond).
- As of Amendment 12, voruciclib will be administered on an intermittent dosing schedule of 3 weeks on/1 week off (IS_{3w,1w}) in the 28-day cycle for Cohorts 21–25. Voruciclib is taken once daily on dosing days only (i.e., Days 1 through 21 on IS_{3w,1w}).
- u. Disease assessment / Bone marrow** – Bone marrow aspirate/biopsy and laboratory evaluation at screening (up to 28 days prior to starting venetoclax), Cycle 2 Day 1, and Day 1 of every subsequent cycle until a CR or CRi is achieved. Thereafter when bone marrow examinations are obtained as clinically indicated, and at EOS. Both biopsy and aspirate are recommended for disease assessment, but biopsy may be omitted if aspirate is considered to be sufficient. Bone marrow assessment may be omitted if the subject has clear evidence of disease progression based of peripheral blood count/blasts analysis. Bone marrow aspirate sample collected at the time of disease assessment may be used for exploratory biomarker analysis in bone marrow/bone marrow aspirate. If any remaining sample is available after evaluation for disease assessment. it should be submitted to the central laboratory for pharmacodynamic biomarker/correlative study (refer to the Lab Manual).

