## 7.2 Baseline Definition

Baseline value for any given parameter is defined as the last assessment obtained prior to the first dose of study drug.

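### In the combination schedule the early Cycle 1 coagulation test (Day 2) falls before voruciclib starts (Day 3), so the first INR/PT/aPTT scheduled on voruciclib is on Day 14

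*Protocol*

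**What the plan says.** **Combination schedule (Protocol Appendix 3).** The row "Coagulation ^p" is marked at Screening, Cycle 1 Day 2, Cycle 1 Day 14, Cycle 2 Day 1, Day 1 of Cycle 3 and later cycles, and End of Study. It is blank on Cycle 1 Days 1, 3 and 8 and on Cycle 2 Day 14. The footnote only lists the panel: "Coagulation – aPTT, PT, and INR". Section 9.7 adds no Cycle 1 timepoint.

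**Monotherapy schedule (Protocol Appendix 2).** The row "Coagulation ^o" has the same early mark on Day 2, then Day 15 and Cycle 2 Day 1. The PK footnote shows what Day 2 means there: "Cycle 1 Day 2: pre-dose (i.e., 24 hours after the Cycle 1 Day 1 voruciclib dose".

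**Voruciclib start in combination (Protocol Section 4.3.2.1).** For Cohorts 12–19: "Voruciclib dosing will be administered on Days 3–14 at the appropriate Cohort Dose". For Cohorts 21–25: "Voruciclib dosing will be administered on Days 3–21 at the appropriate Cohort Dose". Venetoclax starts on Day 1.

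**Why INR is of interest.** Protocol Section 4.14.1 states that "increased INR was a DLT in the previous Phase 1 studies". Section 1 places that event in the 500 mg/day cohort of the continuous-dosing study.

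**Baseline (SAP Section 7.2).** Baseline is "the last assessment obtained prior to the first dose of study drug".

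**The concern.** The Day 2 test has the same position in both AML schedules but a different meaning. In monotherapy it is an early on-drug sample. In combination it is taken before any voruciclib, after venetoclax has started, so it is neither an early voruciclib reading nor a baseline.

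Two things are at stake. The first is DLT ascertainment. Protocol Section 4.4 counts an asymptomatic non-haematological laboratory abnormality of Grade 3 or worse if it does not improve within 72 hours, and Cycle 1 is the DLT window. Between the first voruciclib dose and Day 14, no scheduled sample looks for such an abnormality in coagulation. The second is the reference value. The coagulation baseline is the screening result, which may be up to 28 days old.

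**Working it through.** **Inputs.** Marks come from the Coagulation rows of Appendices 2 and 3. Dosing days come from Section 4.3.2.1 and Tables 5 and 6: Days 3–14 (IS2w,2w once daily), Days 3, 5, 7, 9, 11 and 13 (Cohort 12), and Days 3–21 (IS3w,1w). The Cycle 1 visit window is ±3 days (Appendix 3, footnote a). Effective half-life is 24 to 36 hours (Section 4.3.2.2).

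**Step 1: voruciclib doses on days before each timepoint.**

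| Timepoint | Coagulation marked? | IS2w,2w QD | Cohort 12 (QOD) | IS3w,1w QD |
|---|---|---|---|---|
| Cycle 1 Day 2 | Yes | 0 | 0 | 0 |
| Cycle 1 Day 8 | No | 5 | 3 | 5 |
| Cycle 1 Day 14 | Yes | 11 | 6 | 11 |
| Cycle 2 Day 1 | Yes | 12 | 6 | 19 |

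In monotherapy the Day 2 count is 1. From first dose to first on-voruciclib test is 14 − 3 = 11 days.

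**Step 2: where the other tests fall.** Cycle 2 Day 1 follows a voruciclib-free interval of 14 days on IS2w,2w (Days 15–28) or 7 days on IS3w,1w (Days 22–28). Later cycles are tested on Day 1 only. Cycle 2 Day 14 draws CBC and chemistry but not coagulation. End of Study is about 30 days after the last dose. Cycle 1 Day 14 is therefore the only test within a voruciclib dosing period, restart days aside. In Cohort 12 no dose is given on Day 14. The ECG and pharmacodynamic footnotes move that cohort's sampling to Day 13; the coagulation footnote does not.

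**Step 3: effect of the visit window.** A Day 2 visit held at +3 days is Day 5, after 2 once-daily doses. A Day 14 visit held at −3 days is Day 11, after 8 doses, giving a gap of 11 − 3 = 8 days. Held at +3 days it is Day 17, giving 17 − 3 = 14 days and, on IS2w,2w, a sample after dosing has stopped.

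**Step 4: exposure on Day 8.** The protocol's half-life comes from accumulation ratio R = 1/(1 − exp(−k·24)), so t½ = 24·ln 2 / (−ln(1 − 1/R)). R = 2.06 gives 25.0 h and R = 2.77 gives 37.1 h, in line with the stated 24 to 36 h. The fraction of steady state after n daily doses is 1 − 2^(−24n/t½):

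- n = 5 (Day 8): 0.969 at 24 h and 0.901 at 36 h, or 0.964 and 0.893 with the unrounded half-lives.
- n = 11 (Day 14): above 0.99 in each case.

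This describes drug accumulation only.

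**Step 5: comparison with other rows.** Pharmacodynamic blood is marked on Day 2 in Appendix 2 and on Day 3 in Appendix 3. Appendix 3 also marks ECG, CBC and vital signs on Day 3. The early coagulation mark stayed on Day 2.

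**The case against.** **The Day 2 sample may be deliberate.** A value on venetoclax but before voruciclib could help attribution, since investigators must judge each event against both drugs. The coagulation row was also edited: its mid-cycle test moved from Day 15 to Day 14. A reader might infer that the Day 2 mark was simply copied from monotherapy. The matching mark suggests this, but no document says so, and the mismatch does not depend on it. Equally, no document gives an attribution purpose for the sample.

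**The risk is limited at these doses.** The INR DLT and the related INR SAE were both in the 500 mg/day continuous cohort and may be one event. The maximum here is 350 mg, given intermittently. At 350 mg continuous the DLT reported was diarrhea. No combination DLT had been reported up to 250 mg on IS2w,2w when Amendment 12 was issued. Warfarin users are excluded and entry limits apply to PT and aPTT. All of this stands and limits severity.

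**The gap is nominal.** A reader might infer that a coagulation DLT cannot be detected before Day 14. That goes too far. The window can bring a sample forward, though it can also delay one; investigators can test off schedule, and the SAP provides for unscheduled results. Day 14 lies inside the 28-day DLT window at near-full exposure, so a sustained effect should be seen. Judging the 72-hour clause would need repeat testing whichever day is marked.

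**Day 8 is not a restoration.** Monotherapy has no Day 8 coagulation test either. A reader might also infer that Day 8 would reveal an INR effect six days sooner. The documents give no time course for INR, so only the exposure statement is supported.

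**Moving Day 2 alone has a cost.** It removes the only scheduled value between screening and the first voruciclib dose. This is right, and is why a Day 1 draw belongs in the fix.

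**Conclusion.** The point holds as a mismatch in the schedule. In all combination cohorts the early coagulation test precedes voruciclib and does not meet the SAP baseline definition. On the nominal schedule the first on-voruciclib result is on Day 14: 11 days after the first dose, with 11 earlier doses in once-daily cohorts and all 6 in Cohort 12. On IS2w,2w that is the end of the dosing period; on IS3w,1w seven dosing days remain.

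This rests on nominal visit days and on taking venetoclax as the first study drug in combination, as Protocol Section 6.1 does for adverse events. The consequence is for safety monitoring and DLT ascertainment. No escalation rule or planned efficacy analysis changes, and SAP Section 8.7.3 names haematology and chemistry, not coagulation, in its laboratory summaries. The documents do not show an INR risk at the doses studied here. They show that the protocol names the signal and then schedules its early test on a day that cannot reflect voruciclib.

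**What to change.** Reconcile the Appendix 3 coagulation row with the Day 3 voruciclib start:

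- Place the early Cycle 1 mark at an existing visit after voruciclib has begun. Day 8 is one example: it already draws CBC and chemistry.
- Add coagulation to the Day 1 pre-dose bloods, so that a recent value satisfies SAP Section 7.2.
- State in the footnote how Cohort 12 is handled on Day 14, as the ECG and pharmacodynamic footnotes do.
- If the Day 2 value is wanted for attribution to venetoclax, say so in the footnote and keep it in addition.

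Cost: one mark moved and one extra tube at an existing draw, plus one further test if Day 2 is also kept. There is no new visit, and no dose or treatment rule changes.
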